# 20.5. Assessment of SAEs by the Principal Investigator (or delegate)

The site Principal Investigator (PI) (or delegated individual) is responsible for assessing all reported serious adverse events for reason for seriousness, causality and expectedness.

## Relatedness/causality

The assessment of "relatedness" to the study intervention is the responsibility of the PI at site or an agreed designee according to the following definitions (Table 5):

For the purpose of safety reporting the intervention is defined as lumbar fusion surgery (LFS) or best conservative care (BCC).

Relationship to intervention	Attribution (Causality)	Description
Unrelated	Unrelated	The AE is clearly NOT related
		to the intervention
	Unlikely	The AE is doubtfully related to
		the intervention
Related	Possibly	The AE may be related to the
		intervention

## Table 5: Adverse event causality reporting

Probably The AE is likely related to the	
	intervention
Definitely	The AE is clearly related to the
	intervention

## 20.6. Review of SAEs by the Sponsor/CTU Nominated Person

An appropriately qualified person will review the SAE and raise any queries with the reporting site. If the site has not provided an assessment of causality and has not responded to the query, it will be assumed that the event reported is related to the study procedures/intervention. The site will be encouraged to respond and if a response is not provided the CI will be consulted by the CTU and the CTU will complete the sponsor part of the SAE form.

# 20.7. Reporting of SAEs to the Research Ethics Committee (REC)

All SAEs that are assessed as related and unexpected will be submitted to the REC within 15 days of the CTU/Sponsor becoming aware of the event.

# 20.8. Unblinding of SAEs for reporting to the REC

Not applicable. There is no blinding in this study.

## 20.9. Follow-up of Serious Adverse Events

If the SAE is an Unexpected Serious Adverse Event, then follow up information must be provided as requested by the study office. A follow-up report must be completed when the SAE resolves, is unlikely to change, or when additional information becomes available.

## 21. PREGNANCY

If a participant does become pregnant during this study, it does not need to be reported due to the nature of the intervention of this study as concluded in the risk assessment of the study.

# 22. STATISTICAL CONSIDERATIONS

## 22.1. Statistical Analysis Plan (SAP)

The statistical aspects of the study are summarised here with details fully described in a statistical analysis plan (SAP) that will be drafted early in the study and finalised prior to the final analysis data lock, or any planned interim comparative analyses. The SAP will be written by the Study Statistician in accordance with the current OCTRU SOPs. The SAP will be reviewed and will receive input from the TSC and DSMC.

## 22.2. Sample Size/Power calculations

A total of 270 participants (135 per arm) will be recruited. The sample size estimate is based on a between arm target difference of 8 points on the ODI with a standard deviation of 18, as observed in similar populations  using a 2-sided 5% significance level, 90% power and allowing for up to 20% loss to follow-up. The target difference is considered important by our PPI group, is smaller than the commonly accepted MCID of 10 points,  to allow for some dilution of the treatment effect due to protocol deviation (including some modest crossover from LFS to BCC) and corresponds to a moderate effect size of 0.44.

In this trial, we expect to observe a zero cross-over rate compared to other surgical intervention trials. LFS is not currently offered on the standard NHS pathway, and we expect only those participants randomised to LFS to progress to this surgery within the trial, so the surgical intervention (i.e. LFS) is not, and will not be, accessible to those randomised to BCC. We expect that only a low number of participants randomised to LFS may not undergo their randomised procedure, but we will keep this under review as part of trial monitoring.

# 22.3. Description of Statistical Methods

Standard descriptive statistics will be used to summarise the baseline characteristics by treatment group using means and standard deviation or median and interquartile range for continuous variables, as appropriate, and numbers and percentages for binary or categorical variables.

Unless stated otherwise, analyses and summaries will be based on the as-randomised population, whereby participants will be analysed in line with their randomisation allocation regardless of adherence to the study protocol.

Results will be reported in line with the CONSORT statement and any appropriate extensions and will be described fully in a separate Statistical Analysis Plan. A single final unblinded statistical analysis will take place after all follow-up has been completed, and sufficient time has been allowed for data collection and cleaning.

It is anticipated that all statistical analyses will be undertaken using Stata (StataCorp LP, www.stata.com) or other well-validated statistical packages.

## **Primary Outcome**

The primary outcome measure is the ODI, which will be summarised descriptively by trial arm at baseline and all follow-up time-points. Differences between the trial arms will be estimated using multilevel mixed effects regression model, allowing for repeated measures clustered within participants. The model will be adjusted for the number of levels indicated for spinal fusion (1 or 2 levels), baseline ODI (fixed factors), randomising site (random factor) and other important prognostic factors as appropriate. All covariates will be pre-specified in the statistical analysis plan. A treatment by time interaction will be included. Time will be used as a categorical variable, indicating the protocol stipulated follow-up time point for assessment.

Adjusted mean differences between the groups will be presented together with 95% confidence intervals and p-values, with focus on the between intervention effect at 24 months (primary follow-up time-point).

A number of sensitivity analyses will be performed:

Complier average-causal effect analysis  will be used to evaluate the counterfactual causal effect of LFS, the treatment effect based on time from intervention, area under the curve analysis, and the per-protocol population and consider the type of conservative care received in BCC.

Sensitivity analyses will investigate the effect of missing data on results, including analyses for informative drop-out, whereby participants with missing outcomes will be assumed to have worse outcomes than participants with available data. These sensitivity analyses will be implemented using pattern mixture models using Stata's 'rctmiss' command or similar.

## Secondary outcomes

Secondary outcomes will be analysed using multilevel mixed effects regression models in line with the primary analysis.

Adverse events will be presented descriptively.

# 22.4. Inclusion in analysis

All analyses will be on an intention-to-treat basis. This means that participants will be analysed as they are randomised irrespective of the treatment actually received. The intention-to-treat population will include participants who have given their informed consent, for whom there is confirmation of successful allocation of a randomisation number, and for whom at least one follow-up assessment is available. The principal analyses will not include imputation for missing data.

A per protocol population will exclude participants who did not receive their randomised intervention. Details of additional exclusions from this analysis population will be defined in the statistical analysis plan.

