#### **Medical notes check**

The central study team will follow up any complications reported by participants with the local research team at participating sites. Details will be collected and recorded on a complications form.

In addition, a final readmission checklist will be undertaken by the research staff on participating site records at 24 months post-randomisation to ensure that all complications data are collected from all participants (i.e. those who had not returned a questionnaire). Data from any readmission events e.g. revision/further surgery identified will be recorded on the Complications Form.

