# 22.9. Procedure for accounting for missing data

The procedure for handling spurious or missing data will be described in the Statistical Analysis Plan, and the Data Monitoring and Sharing Plan. The study will attempt to collect data as completely as possible.

Missing data will be minimised by careful data management, information provided to participants and training of study staff. Missing data will be described with reasons given where available; the number and percentage of individuals in the missing category will be presented by intervention arm. All data collected on the database will be used, since only essential data items will be collected. No data will be considered spurious in the analysis since all data will be checked and cleaned before analysis. The primary analysis will utilise all available data, and participants with at least one follow-up data point will be included in analyses. No imputation for missing data is planned, and sensitivity analyses will investigate the effect of missing data on the results, including analyses for informative drop-out.

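### Section 22.4 puts every analysis on a population that needs at least one follow-up assessment, which conflicts with the as-randomised default in 22.3 and, read literally, could drop an early severe harm from the complications summary

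*Protocol*

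**What the plan says.** Three parts of the Protocol describe who is analysed.

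- Section 22.3: "Unless stated otherwise, analyses and summaries will be based on the as-randomised population". Participants are kept in their allocated arm whatever their adherence. No follow-up condition is attached.
- Section 22.4: "All analyses will be on an intention-to-treat basis". The population is then restricted to people who consented, have a confirmed allocation, "and for whom at least one follow-up assessment is available". The section also defines a second set: "A per protocol population will exclude participants who did not receive their randomised intervention".
- Section 22.9: "The primary analysis will utilise all available data, and participants with at least one follow-up data point will be included in analyses".

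On harms, section 9.2 counts surgical complications, further surgery including re-admission, and complications of conservative care among the further secondary outcome measures. Its outcome table lists complications data, including re-admissions, as item 9. Section 22.3 models secondary outcomes in line with the primary analysis and adds: "Adverse events will be presented descriptively". No population is named for that presentation.

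On collection, section 20.1 starts safety reporting at first administration of the intervention. The medical notes check in section 17.3, repeated in section 20.3, has sites search their records at 24 months "to ensure that all complications data are collected from all participants (i.e. those who had not returned a questionnaire".

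**The concern.** Section 22.4 calls its population intention-to-treat but makes membership depend on something observed after randomisation. For a repeated-measures model of the Oswestry Disability Index this matters little, because a person with no follow-up score adds nothing to the likelihood. For harms it matters, because the harm can itself be the reason that no follow-up assessment exists. Section 20.3 lists death, stroke and cauda equina syndrome among the expected complications of surgery. If the 22.4 condition governs the complications summary, a participant with such an event before any follow-up is lost from both numerator and denominator. The loss would fall mainly on the arm in which these events are expected. The protocol would also have collected, through the 24-month record check, data that its own analysis rule sets aside.

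**Working it through.** **1. The denominator.** Section 22.2 gives a difference of 8 points, SD 18, two-sided 5%, 90% power and 20% loss. The normal approximation is n = 2 × (1.960 + 1.282)² × 18² / 8² = 106.4, so 107 per arm. Then 107 / 0.80 = 133.75, so 134 per arm and 268 in total. The stated 270 (135 per arm) reproduces to within 2 participants. The sample size is not in question, and 135 is the arm size used below.

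**2. The texts side by side.**

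- 22.3: covers analyses and summaries; everyone randomised; no follow-up condition; yields where something else is stated.
- 22.4: covers all analyses; at least one follow-up assessment required; no exemption for harms.
- 22.9: at least one follow-up data point, in a sentence that opens with the primary analysis.

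The 22.3 default yields to contrary statements, and 22.4 is arguably one. The two sections therefore name different populations. Section 22.4 also conflicts with its own principle of analysing people as randomised, because a set selected on later data is no longer everyone randomised.

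**3. Does the condition reach harms?** Complications and re-admissions are secondary outcomes (9.2), and secondary outcomes follow the primary analysis (22.3). Expected procedure-related adverse events are collected as complication data (20.3). On that chain the 22.4 population applies. Against it, the adverse-event sentence names no population, and a descriptive presentation is a summary of the kind covered by the 22.3 default.

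**4. What counts as a follow-up assessment?** The term is not defined, and three readings are open.

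- *The 6-, 12- and 24-month questionnaires only.* Anyone who never returns one is excluded. Someone harmed early who later returns any questionnaire stays in.
- *Any participant-reported score, including the monthly pain rating.* Only people with no score at all are excluded, for example after a very early death.
- *The medical notes check as well.* Section 17.2.3 lists it under follow-up, and Table 2 lists safety reporting and complication data at 6, 12 and 24 months. The condition then excludes almost nobody, apart perhaps from people who withdraw fully. It also no longer identifies who has outcome data.

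**5. Size, as arithmetic only.** Suppose E of N participants have the event and k of those E have no follow-up assessment, with everyone else retained. The reported risk is then (E − k)/(N − k) instead of E/N.

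- E = 1, k = 1, N = 135: 0/134 = 0% (exact 95% CI 0 to 2.7%) instead of 1/135 = 0.7% (0.02% to 4.1%).
- E = 10, k = 1: 9/134 = 6.7% instead of 10/135 = 7.4%.
- E = 10, k = 2: 8/133 = 6.0% instead of 7.4%.

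The values of E and k are assumed. The protocol gives no complication rate and no figure for participants with no follow-up of any kind. Its 20% allowance is for loss to follow-up in the sample size, which is a different quantity.

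**The case against.** The strongest reply is that the protocol never says adverse events are confined to the 22.4 population. Section 22.3 has a default that covers summaries, section 22.9 places the follow-up rule in the sentence on the primary analysis, and the record check shows the intent to count complications in everyone. To collect those data and then discard them is the least plausible intention. This stands as an account of what the authors probably meant. It does not remove the wording in 22.4, which covers all analyses without exception.

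The second reply is that the problem case is rare. Pain is scored monthly. Surgical participants join routine waiting lists (13.1), and section 9.3 chose 24 months with those waits in mind, so many will have supplied follow-up data before their operation. Non-responders to the questionnaires are also telephoned (17.3). This stands too, and it keeps the likely number very small.

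The third reply is that safety populations belong in the statistical analysis plan, which is not at hand. That is right, and the lack of a named safety population is not a fault here. The point is that the protocol fixes a rule for all analyses, and a later safety set of all randomised participants would contradict that rule as worded.

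A reader might infer more: that 22.4 defines the only analysis population, or that early deaths will be removed from safety reporting. Neither is supported. Section 22.3 gives an as-randomised default, 22.4 itself adds a per-protocol set, and exclusion from the adverse-event tables is only one reading. Expedited reporting of serious adverse events and review by the Data and Safety Monitoring Committee do not depend on the 22.4 population.

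**Conclusion.** The inconsistency is real and should be corrected. Sections 22.3 and 22.4 name different populations, and 22.4 makes an intention-to-treat set conditional on follow-up. Because complications and re-admissions are secondary outcomes, a literal reading could leave out a participant with an early severe harm and no follow-up assessment, against the evident purpose of the 24-month record check.

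The likely effect is very small in number: perhaps no participant and at most a few, a judgement that assumes monthly scores, later questionnaires or the notes check count as follow-up. It still matters, because a single grave event can change how a rare harm reads, as 0/134 against 1/135 shows. A material bias of the benefit-harm comparison towards surgery might be inferred, but it cannot be shown: no percentage of complications lost can be derived from the protocol, and any such figure would rest wholly on assumed non-response and event rates.

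**What to change.** In section 22.4, limit the requirement for at least one follow-up assessment to the participant-reported outcome models, and make the same limit explicit in section 22.9. Add that complications, re-admissions, serious adverse events and deaths are summarised for all randomised participants, whether or not any questionnaire or pain score was returned, and that events found in the 24-month record check are included. Reword 22.3 or 22.4 so that both name the same default population. Whether to tabulate by treatment received as well can be left to the statistical analysis plan.

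The cost is a sentence or two and no new data, because the record check already covers all participants. The small downside is that harms are less completely ascertained in people known only from that check, which a table footnote can say.

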# 22.5. Subgroup analysis

Consistency of the treatment effects for important subgroups (including the number of levels indicated for spinal fusion (1 or 2 levels) and baseline ODI categories) will be explored. A full list of subgroups to be explored will be provided in the statistical analysis plan. Subgroup effects with 95% CIs will be obtained from linear regression models for the 24-month primary outcome, adjusted in line with the principal analysis and an interaction between randomised intervention and subgroup. We will also explore the effect of delayed intervention (both LFS and BCC) on the observed ODI outcomes. Findings will be presented graphically and viewed as exploratory.

## 22.6. Interim analyses

The main outcomes will be analysed as stated in the analysis plan once the study follow-up has been completed. No formal interim analyses of treatment effect are planned for any of the study outcomes.

# 22.7. Stopping rules

As no formal interim analyses are planned, no stopping rules have been incorporated into the study design. An independent Data and Safety Monitoring Committee (DSMC) will review the accumulating data at regular intervals and may recommend pausing or stopping the study in the event of safety concerns, as specified in the DSMC Charter. The TSC will make any final decision to terminate the study if appropriate.

# 22.8. Level of Statistical Significance

All treatment comparisons will be reported with 95% confidence intervals and a significance level of 5% will be used to test statistical significance.

# 22.9. Procedure for accounting for missing data

The procedure for handling spurious or missing data will be described in the Statistical Analysis Plan, and the Data Monitoring and Sharing Plan. The study will attempt to collect data as completely as possible.

Missing data will be minimised by careful data management, information provided to participants and training of study staff. Missing data will be described with reasons given where available; the number and percentage of individuals in the missing category will be presented by intervention arm. All data collected on the database will be used, since only essential data items will be collected. No data will be considered spurious in the analysis since all data will be checked and cleaned before analysis. The primary analysis will utilise all available data, and participants with at least one follow-up data point will be included in analyses. No imputation for missing data is planned, and sensitivity analyses will investigate the effect of missing data on the results, including analyses for informative drop-out.

# 22.10. Procedures for reporting any deviation(s) from the original statistical analysis plan

Any changes or deviations to the original SAP will be described and justified in the protocol, final statistical report and/or publications, as appropriate to the timing of the changes.

# 23. HEALTH ECONOMICS

The health economics aspects of the study are summarised here, and full details will be described in a Health Economic Analysis Plan (HEAP) that will be drafted and finalised prior to the final analysis data lock. The HEAP will be written by the study lead Health Economist and will be reviewed and will receive input from the TSC.

# 23.1. Within trial economic evaluation

An economic evaluation will be undertaken alongside the trial to estimate the cost effectiveness of LFS versus BCC. This will take the form of an incremental cost-utility analysis to estimate cost per quality adjusted life year (QALY) and incremental net benefit at 24 months follow-up, using patient level data on costs and outcomes from the trial. The base-case analysis will be from an NHS perspective, with an additional analysis from a societal perspective taking into account out of pocket expenditure and productivity losses. In order to calculate QALYs, the EQ-5D-5L will be included in the questionnaires to participants at baseline, 6, 12 and 24 months. The UK mapping value  set will be applied to participant responses to obtain utility scores, in line with current NICE recommendations.

Data will be collected within the trial to calculate the cost of each LFS undertaken. Information will be collected via the surgery CRF on the type of surgery undertaken and length of stay post-operation and will be used to attach the relevant Healthcare Resource Group (HRG) code from the most recent NHS reference costs. Any additional post-operative resource use will be collected via the participant completed follow-up questionnaires. For each participant allocated to BCC, their package of care will be recorded, including types of care (e.g. a course of physiotherapy, multidisciplinary pain management programme), mode and number of sessions. The per-person cost of BCC will then be calculated.

Information on all other LBP-related resource use will be collected via participant questionnaires at 6, 12 and 24 months. Questions will request information regarding primary and secondary care visits (e.g. GP, nurse, physiotherapy, consultant, specialist, outpatient clinic), visits to other healthcare professionals including non-NHS, prescribed analgesics, tests and investigations, further treatment including surgery and injections. The recall period in each questionnaire will be the previous 6 or 12 months. Unit costs from standard UK sources will be sought for all healthcare resource use items.

Data on broader costs will also be collected, related to both out of pocket expenditure (e.g. private health care or pain relief items such back supports, TENS machines) and time off work to calculate productivity losses. Information on occupation group and the nature of their employment (full time or part time) will be sought. The average wage for each respondent will be identified using UK Standard Occupational Classification coding and annual earnings data for each broad job type.

